#### *Rationale for Sample Size*

The sample size calculation is based on statistical considerations for the analysis of the primary endpoint. With 45 subjects per arm, 85% power is achieved to detect a 50% reduction in median time-to-BQL (0.5 day with ALX-0171 versus 1 day with placebo) for the plaque assay using a two-sided log-rank test at significance level of 0.05. For each comparison of the ALX-0171 dose groups with placebo, a significance level of 0.05 is assumed. For multiple pairwise comparisons, the family-wise error rate is controlled at 5% through the closed testing principle, where the comparison of the lower dose of ALX-0171 to placebo is only performed if the comparison of the higher dose of ALX-0171 to placebo is significant. The sample size calculation also assumes a drop-out rate of 15% to account for subjects dropping out prior to reaching the primary endpoint, or due to a false positive RSV test.

Change from baseline in Global Severity Score is a secondary endpoint of interest in this study. With this sample size, a power of 80% is achieved to detect a difference of 2 points

in the mean change from baseline (to Day 2 post-dose) on the Global Severity Score for each of the ALX-0171 dose groups to placebo. This is based on a two-sided t-test with a significance level of 0.05 and assuming a common standard deviation of 3.2 in each group.

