## 4.2 Sample size

With 45 subjects per arm, 85% power is achieved to detect a 50% reduction in median time-to-BQL (0.5 day with ALX-0171 versus 1 day with placebo) for the plaque assay using a two-sided log-rank test at significance level of 0.05. For each comparison of the ALX-0171 treatment groups with placebo, a significance level of 0.05 is assumed. For multiple pairwise comparisons, the family-wise error rate is controlled at 5% through the closed testing principle, where the comparison of the lower dose of ALX-0171 to placebo is only performed if the comparison of the higher dose of ALX-0171 to placebo is significant. The sample size also incorporates a 15% drop-out rate. With this sample size, a power of 80% is achieved to detect a difference of 2 points in the mean change from baseline (to Day 2 post-dose) on the Global Severity Score for each of the ALX-0171 treatment groups to placebo. This is based on a two-sided t-test with a significance level of 0.05 and assuming a common standard deviation of 3.2 in each group.

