### 7.1 Primary Efficacy Endpoint Evaluation

The primary endpoint for this trial is the time needed for the viral load to drop below the plaque assay quantification limit (time-to-BQL) in nasal mid-turbinate swab specimens. Time to BQL is defined as the time from the reference point (first dosing) to the first occurrence of a value below the limit of quantification, provided the next measured value is below the limit as well. The time to event for subjects with missing data and/or who did not reach BQL during the trial will be censored at the last nonmissing viral load assessment .

The time-to-BQL will be compared between each of the ALX-0171 treatment groups and the combined placebo group using a log-rank test. The null hypothesis of this test assumes no difference in time-to-BQL between Placebo and ALX-0171 treated subjects. The tests will be performed in a sequential way to preserve the family-wise error rate at 0.05. Specifically, dose 3 (highest dose) of ALX-0171 will first be tested against the combined placebo group at the 0.05 significance level. Dose 2 of ALX-0171 will only be compared to placebo at the 0.05 significance level if the comparison of dose 3 with placebo is significant. Consequently, dose 1 of ALX-0171 will only be compared to placebo at the 0.05 significance level if the comparison of dose 2 of ALX-0171 with placebo is significant. The primary efficacy endpoint will be evaluated using the mITT population.

The logrank test is based on the assumptions that censoring is unrelated to prognosis and the event probabilities are the same for subjects recruited early and late in the study. Kaplan-Meier (KM) estimates on time-to-BQL will be tabulated (Median, 25th, 75th percentile with confidence interval and general information on censoring) and a graph of the Kaplan-Meier survival curve will be presented.

The data will also be analyzed using a Cox proportional hazards regression model with time to BQL as dependent variable, and treatment group, viral load at baseline and co-infected subject group as independent variables. The hazard ratio (HR) from the Cox model along with the 95% CI will be reported. This analysis will only be performed for the treatment groups where the comparison was significant as analyzed by the log rank test.

For sensitivity analyses, the primary endpoint will also be evaluated using:

- the RSV Infected population
- the Per Protocol population.

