## 13 CHANGE FROM ANALYSIS PLANNED IN PROTOCOL

Additional analysis on the primary endpoint was added using a Cox proportional hazards regression model with time to BQL as dependent variable, and treatment group, viral load at baseline and co-infected subject group as independent variables. These changes will not lead to an amendment of the clinical trial protocol

Following endpoints were added:

- Time between first study drug administration and discharge
- Duration of severe disease
- Duration of feeding support
- Subgroup analyses have been added for selected efficacy and safety endpoints

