## 16.2 Efficacy

**Table 14.2.1.1: Primary Endpoint: Time to below quantification limit of RSV viral load (plaque assay) (T)**

Kaplan-Meier analysis, including a two-sided Log-rank test. The output will include number of events, number of censored values, median, 25% percentile and 75% percentile of time to event with 95% CIs and p-value of the log-rank test. Additionally the results of a Cox proportional hazards regression model with time to BQL as dependent variable, and treatment group, viral load at baseline and co-infected subject group as independent variables will be reported including Hazard ratio (95% CI) and p-value

Population: mITT population.

**Table 14.2.1.2: Sensitivity analysis - Time to below quantification limit of RSV viral load (plaque assay)-RSV Infected population (T)**

Kaplan-Meier analysis, including a two-sided Log-rank test. The output will include number of events, number of censored values, median, 25% percentile and 75% percentile of time to event with 95% CIs and p-value of the log-rank test. Additionally the results of a Cox proportional hazards regression model with time to BQL as dependent variable, and treatment group, viral load at baseline and co-infected subject group as independent variables will be reported including Hazard ratio (95% CI) and p-value

Population: RSV infected population.

**Table 14.2.1.3: Sensitivity analysis - Time to below quantification limit of RSV viral load (plaque assay)-Per Protocol analysis (T)**

Kaplan-Meier analysis, including a two-sided Log-rank test. The output will include number of events, number of censored values, median, 25% percentile and 75% percentile of time to event with 95% CIs and p-value of the log-rank test. Additionally the results of a Cox proportional hazards regression model with time to BQL as dependent variable, and treatment group, viral load at baseline and co-infected subject group as independent variables will be reported including Hazard ratio (95% CI) and p-value

Population: Per Protocol population.

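### SAP 7.1 limits the primary hazard ratio to doses significant on log-rank, contrary to SAP 13 and the table shells, and the assumptions behind the 85% power are unstated

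*Protocol*

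**What the plan says.** **Hazard ratio.** SAP 7.1 compares each dose with placebo by log-rank test in fixed order: dose 3, then dose 2, then dose 1, each tested only if the one before it is significant. It adds a Cox model with treatment group, baseline viral load and co-infection as terms, and then restricts it: "This analysis will only be performed for the treatment groups where the comparison was significant as analyzed by the log rank test". SAP 13 records the same model as a change from the protocol with no such restriction: "Additional analysis on the primary endpoint was added using a Cox proportional hazards regression model". The shells for Tables 14.2.1.1 to 14.2.1.3 are also unconditional: "Additionally the results of a Cox proportional hazards regression model with time to BQL as dependent variable" and "will be reported including Hazard ratio (95% CI) and p-value".

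**Event date.** SAP 7.1 dates the event at the first BQL swab, provided that the next measured value is also BQL. Otherwise the infant is censored at the last available viral load.

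**Sample size.** Protocol 3.1.2 (Rationale for Sample Size) states that "85% power is achieved to detect a 50% reduction in median time-to-BQL (0.5 day with ALX-0171 versus 1 day with placebo", with 45 per arm and a two-sided log-rank test at 0.05. Its 15% drop-out covers "subjects dropping out prior to reaching the primary endpoint, or due to a false positive RSV test". SAP 4.2 repeats the figure and adds: "The sample size also incorporates a 15% drop-out rate". Neither document gives a hazard ratio, a distribution for clearance times, or an allowance for seeing clearance only at swabs.

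**The concern.** Protocol 3.1.2 says that the study will support choice of the optimal dose. That choice needs an effect estimate with its uncertainty for each dose, above all for doses that miss significance. SAP 7.1 removes the estimate in exactly that case. Because the gate runs from the top dose down, one non-significant result for dose 3 means that doses 1 and 2 are never tested, so they have no significant comparison and no hazard ratio either. When the hazard ratio is reported, it has passed a significance filter and is on average too large.

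The SAP also gives two instructions for one table. A programmer cannot follow both, and the choice should not be made after the results are known.

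The sample-size statement bears on how a non-significant first test is read. A reader who takes 85% at face value will treat it as stronger evidence against a halving than the design supports.

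**Working it through.** **1. The plan's own figure.** Inputs from Protocol 3.1.2: medians 0.5 and 1 day, two-sided 0.05, power 85%, 45 per arm, drop-out 15%. For exponential times, halving the median doubles the clearance rate (HR 2).

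- Schoenfeld events: (1.960 + 1.036)² / (0.25 × (ln 2)²) = 8.976 / 0.1201 = 74.7, so 75 events or 38 per arm.
- With drop-out: 38 / 0.85 = 44.7, so 45 per arm.
- Power at 76 events: Φ(√(76 × 0.25) × 0.693 − 1.960) = Φ(1.061) = 85.6%.

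The 85% therefore reproduces, for exponential times and an exactly dated event in every evaluable infant.

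**2. What remains without a hazard ratio.** SAP 7.1 gives every dose the Kaplan-Meier (KM) median and quartiles with CIs, and the curve. SAP 7.2.2.2 adds percent BQL over time, viral load and its change by visit, and time-weighted average change. None of these is a relative effect with a CI.

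**3. How the medians behave.** Both nebulizations may take up to 4 h (Protocol 3.3.7.2), and the post-dose swab follows at 5 ± 1 h, so the last Day 1 swab is at 4 + 5 + 1 = 10 h at the latest. The Day 2 dose can be as early as 24 − 4 = 20 h, with its swab up to 2 h before, at 18 h. No routine swab falls between about 10 h and 18 h. A Withdrawal-visit swab could.

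Suppose that 12 h and 24 h are underlying exponential medians, with nominal swabs at 5.5, 23, 29.5, 47 and 50.5 h:

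- ALX-0171 cleared by 5.5 h: 1 − 2^(−5.5/12) = 27%. By 23 h: 1 − 2^(−23/12) = 73%. The median reads 23 h.
- Placebo cleared by 23 h: 1 − 2^(−23/24) = 49%. By 29.5 h: 1 − 2^(−29.5/24) = 57%. The median reads 29.5 h.
- Ratio 23 / 29.5 = 0.78, against a true 0.5.

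With swab times varied inside the protocol windows, the simulated medians are about 23 h and 27 to 29.5 h (ratio 0.79 to 0.83). In the same simulations an unadjusted Cox hazard ratio stays near the true 2.0 (1.95 to 2.04).

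**4. How often the condition bites.** Simulation: shared placebo, 45 per arm, 15% drop-out spread over the treatment period with a Withdrawal swab, discharge swab in half of infants, 12,000 runs.

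| True HR, doses 3 / 2 / 1 | Hazard ratios reported under SAP 7.1 |
|---|---|
| 2.0 / 2.0 / 2.0 | none in 19% of trials, all three in 64% |
| 2.0 / 1.75 / 1.5 | all three in 29% |
| 1.5 / 1.5 / 1.5 | none in 62% |

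At a true HR of 2, the mean estimate is 2.07 to 2.19 in significant trials and 1.39 to 1.42 in the others.

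**5. What the 85% depends on.** Assumptions not in the documents: no rebound after clearance, discharge swab at 96 h for 0, 50 or 100% of infants, and the timing of drop-out.

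| Setting | Power |
|---|---|
| 38 per arm, Schoenfeld formula | 85.6% |
| 38 per arm, exact times, simulated | 83.4% |
| 38 per arm, planned swabs with confirmation | 78–80% |
| 45 per arm, 15% lost late or spread over 14 days | 84–86% |
| 38 per arm, planned swabs, Weibull shape 0.8 | 57–61% |
| 38 per arm, planned swabs, Weibull shape 1.2 | 90–92% |

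The 15% also includes false-positive RSV infants. The mITT population (SAP 5.1.3), which is primary, keeps them. Only the RSV Infected sensitivity analysis (SAP 5.1.4) removes them. If they are BQL from the first swab in both arms, simulated power is 75–77% when they make up half of the 15%, and 70–72% when they make up all of it.

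**The case against.** The strongest reply is that little is broken. The 85% is correct arithmetic under a standard assumption, enrolment would not change, and the log-rank test stays valid. The table shells already carry the hazard ratio for every dose, so SAP 7.1 is one side of an inconsistency. The 19% is simply one minus the power at the first test. Every dose keeps its quartiles, curve and viral-load summaries, and the 75th percentile shows a halving better than the median does (about 51 h against 27 to 30 h). All of this stands. It does not answer the conflict between SAP 7.1 and SAP 13, or the absence of a relative effect with a CI.

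Four stronger readings are tempting, and the documents do not support them:

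- *The true power of the primary analysis is about 77–84%.* That range treats all drop-outs as lost, whereas the mITT analysis keeps false positives. It also rests on guessed drop-out and discharge timing and on an exponential shape.
- *The KM medians cannot measure the design effect.* Protocol 3.1.2 states medians of time-to-BQL, which SAP 7.1 dates at a swab. Whether 0.5 and 1 day are underlying or swab-dated times is not said, so a table footnote asserting one reading would go too far.
- *The tie method is a material gap.* Protocol 3.4.3.1 records exact swab times. With times varied inside the windows, Breslow and Efron gave the same hazard ratio (1.97). Breslow's 1.66 to 1.73 arises only if nominal, tied times are used.
- *The Cox result is shown to be unbiased for the planned model.* The simulations did not include the baseline viral load and co-infection terms.

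**Conclusion.** The inconsistency is plain from the text and should be settled before unblinding. As SAP 7.1 is written, failure at dose 3 leaves all three doses without a relative effect and CI on the primary endpoint. Under the simulated conditions that is 19% of trials with a true HR of 2 for every dose and 62% with 1.5. These frequencies rest on exponential clearance and the assumed drop-out pattern. The conflict itself rests on no assumption.

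The power statement is incomplete, not wrong. Reading clearance at swabs costs roughly 3 to 6 points against exact times (83.4% to 78–80% at 38 evaluable per arm), and the result is close to 85% if drop-out is late. The assumed shape matters far more, and retained false positives could lower power further. No single replacement figure for the mITT analysis can be derived from the documents.

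**What to change.** **SAP 7.1.** Keep the log-rank test and the gate as primary. Delete the sentence that makes the Cox model conditional on significance, so that the section agrees with SAP 13 and Tables 14.2.1.1 to 14.2.1.3. Report the planned covariate-adjusted hazard ratio with 95% CI for every dose, using actual swab times. For doses that the gate does not reach, label it descriptive and give no p-value, and adjust the table shells to match. The tie method can be named in the programming specifications.

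**Protocol 3.1.2 and SAP 4.2.** State that:

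- 85% is the Schoenfeld figure for exponential times with HR 2 and about 75 exactly dated events.
- Reading clearance at swabs with next-swab confirmation lowers it by a few points (about 78–80% at 38 evaluable per arm, close to 85% if drop-out is late).
- It depends strongly on the assumed shape of the clearance-time distribution.
- It counts false-positive RSV infants as lost although the primary mITT analysis keeps them, which could lower power further.

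**Cost.** One sentence deleted, a few added, and a little programming. The stated power looks less favourable, and the extra hazard ratios must be clearly labelled so that they are not read as claims. No swabs or infants are added, the primary test and its type I error are unchanged, and the lost power is not recovered.

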#### *Dosing Rationale*

The study drug will be administered along with standard of care treatment, which will be determined by the Investigator (or his/her designee) according to institutional practice††. Study drug will be administered once-daily for 3 consecutive days, similar to the treatment schedule in Study ALX0171-C104. This 3-day treatment period is expected to bridge the time needed for the body to mount an effective immune response. In order to assess a dose response in Study ALX0171-C201, three doses (target dose of 3 mg/kg, 6 mg/kg and 9 mg/kg) will be investigated. This dose range will provide information on the PK, PD and clinical outcomes across a relevant range, is expected to provide a potential benefit to the subjects, and is intended to determine the most optimal dose of ALX-0171 for further clinical development.

Please refer to section [3.3.2](#) for more information on the dose selection.

All doses of study drug will be administered in the hospital setting. Subjects may be discharged from hospital starting from dosing Day 2 onwards, after all required assessments of the 5 hours ( $\pm$  1 hour) post-dose time point have been completed. The decision to discharge is up to the Investigator but can only occur per protocol if the protocol-defined clinical response criteria have been met. Hence, an ambulatory visit will be permitted for the 3rd study drug administration (i.e., subjects need to return to the hospital for the administration of the 3rd dose by the appropriately trained personnel and have their 2 hour pre- and post-dose monitoring period).

Study drug will be administered via inhalation, using a dedicated vibrating mesh nebulizer.

- Vibrating mesh type nebulizers are considered the most appropriate technology for nebulization of a therapeutic protein such as ALX-0171 Nanobody.
- The FOX-Flamingo nebulizer (Vectura GmbH, Germany) was developed concurrently with the study drug. The nebulizer is a battery-operated, hand-held device, intended for single-patient use. The device provides an aerosol with particle size suitable for the intended study population ( $\sim$ 3  $\mu$ m).
- The nebulizer is always to be used with a flow of 2 L/min additional air or O2 (to be decided by the Investigator based on oxygen need of the subject).

The formulation of ALX-0171 (and matching placebo) was developed specifically as a liquid solution for inhalation, to ensure rapid delivery of the study drug to the site of RSV infection, and to maintain product quality and stability in combination with the nebulization protocol.

- The formulation buffer is comparable to a normal 0.9% saline solution with respect to salt content but has additional buffering capacity. The osmolality and ion concentration of the (isotonic) solution were chosen to be within the physiological range. The phosphate buffer system helps to maintain a constant pH, and therefore, to guarantee the stability of the drug.
- All excipients comply with the European Pharmacopoeia and the United States Pharmacopoeia.
- The formulation contains no antimicrobial preservatives or tension active agents (surfactants), and no coloring agents, flavors, or sugars/sweeteners are present. Correspondingly, the nebulizer solution does not have a specific taste or odor.

The use of formulation buffer as placebo is considered appropriate, taking into account that formulation buffer is the most representative control for the active study drug, while the minute amounts of phosphate present in the buffer would not be expected to result in effects different from saline. Throughout the clinical studies conducted with ALX-0171 and placebo, there were no consistent findings that would suggest a direct effect of the formulation buffer on respiratory parameters.

Details on initiation, interruptions and completion of study drug administration, will be collected in the electronic case report form (eCRF), as will the acceptability of the face mask and nebulizer and whether or not correct administration was achieved (also see section [3.3.7](#)).

### **3.1.3. BLINDING**

To ensure blinding across dose groups, study drug will be administered via inhalation using 2 serial nebulizations. These two nebulizations will consist either of two nebulizations of ALX-0171, or one of ALX-0171 and one of placebo, or two nebulizations of placebo depending on the assigned treatment group (see section [3.3.7](#)).

In order to protect the integrity of the data, treatment assignment will be kept blinded for investigative sites, subjects, subject's parent(s)/legal guardian(s) and caregiver(s), site monitors, and other members of the study team, until after the final database lock (i.e., after the last subject has completed the final [EOS] visit and all data is considered clean). Identification of Sponsor and contract research organization (CRO) personnel who will have access to unblinded data (e.g., PK sample analysis team) during the course of the study will be documented prior to unblinding. The number of Sponsor personnel having access to the data will be limited.

**Ablynx NV****Clinical Study Protocol ALX0171-C201****Final v3.0**

---

**Emergency unblinding procedure**

Code-breaking and unblinding in the event of medical emergencies can be done by the Investigator via the Interactive web/voice response system (IWRS/IVRS), which will be accessible 24 hours per day/7 days per week.

Unblinding by the Investigator should occur only in the event of an AE for which it is necessary to know the study treatment to determine an appropriate course of therapy for the subject. The Investigator should first discuss options with the Medical Monitor if possible with due consideration of the safety of the subject. If the Investigator must identify the treatment assignment of an individual subject, the Principal Investigator/Sub-investigator is to contact the IWRS/IVRS.

Subjects for whom the code has been broken by the Investigator will have to discontinue study drug treatment and subjects will be followed up according to the in-hospital post-treatment period (if applicable), FU visit and EOS visit.

## 3.2. SELECTION OF STUDY POPULATION

Infants and young children of both genders, diagnosed with and hospitalized for RSV LRTI but otherwise healthy, are eligible for this study. Approximately 180 subjects are planned to be enrolled in the study.

### 3.2.1. INCLUSION CRITERIA

A subject will be eligible for study participation if he/she meets all of the following criteria at screening and randomization, unless specified otherwise:

1. Subject is a male or female infant or young child aged 28 days to <2 years with gestational age  $\geq$  33 weeks at screening.
2. Subject weighs between  $\geq$  3.0 kg and < 15.0 kg at screening.
3. Subject is otherwise healthy, but is hospitalized for and clinically diagnosed with RSV LRTI (bronchiolitis or broncho-pneumonia), i.e., showing typical clinical signs and symptoms such as tachypnea, wheezing, cough, crackles, use of accessory muscles and/or nasal flaring.
4. Subject has a positive RSV diagnostic test at screening.##
5. Subject is expected to have to stay in the hospital for at least 24 hours (according to the Investigator's judgment at screening).
6. Symptoms likely related to RSV infection (i.e., the symptoms present need to be probably linked to the current RSV infection according to Investigator's judgment) have appeared within 4 days of screening and are not yet improving at screening and randomization.
7. Subject fulfils at least two of the following RSV disease severity criteria at screening and randomization:
  - Inadequate oral feeding that requires feeding support (i.e., nasogastric tube or i.v. line)
  - Inadequate oxygen saturation defined as:
    - Oxygen saturation ( $SpO_2$ )  $\leq$  92% on room air or
    - Requiring oxygen supplementation to maintain oxygen saturation  $>$  90% with documented pre-supplementation value  $\leq$  92%
  - Signs of respiratory distress defined as:
    - Respiratory rate  $\geq$  50 per minute in infants up to 12 months of age, and  $\geq$  40 per minute in children above 12 months and/ or
    - Moderate or marked respiratory muscle retractions

---

## RSV infection will be confirmed either according to routine site practice (PCR or diagnostic quick test), or using a (Sponsor-provided) commercial kit.

8. Subject has normal psychomotor development.
9. Parent(s)/legal guardian(s) provide written informed consent in accordance with locally approved consent process at screening.
10. The parent(s)/legal guardian(s) are able and willing to comply with the study protocol procedures.

